Study Title:
**Social Ecological Based Smoking Cessation Intervention in Public Housing
Neighborhoods**

R01HL090951

Date: 8/09/2018

Statistical Analyses.

Preliminary Analysis. Univariate descriptive statistics and frequency distributions will be calculated as appropriate for all variables. These analyses will identify departures from distributional assumptions for proposed procedures. If departures are identified, appropriate transformations of data will be applied, or alternative analysis procedures (e.g., semi-parametric or nonparametric) will be employed. Baseline values for demographic and other putative prognostic variables will be compared for imbalance across the two treatment conditions (TX, C). These analyses will identify potential confounding variables to be used as covariates in subsequent analyses. Putative prognostic variables that will be investigated through these descriptive analyses include age, income, education, nicotine dependence score, and depression score. *To investigate potential limits on generalizability, we will compare demographic and other baseline characteristics of the dropouts with those who were completers.*

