In further analyses, putative covariates will be added to the model to examine whether the intervention remained statistically and clinically associated with cessation after controlling for the potential covariates. Each covariate considered for inclusion will be examined individually for a relationship with cessation outcomes. In the second step, those variables with a p value < .25 will be included in an initial model. Next, the potential confounder variable in the initial model with highest p value will be removed and the model will be run again. If the removal of the potential confounder variable does not result in a significant reduction in model fit (as indicated by a change in the model -2 log likelihood), then the variable is removed from further steps. The removal and subsequent testing of change in model fit will be repeated until all non-significant potential confounders are tested. Potential covariates include demographic variables (i.e., age, income, education), nicotine dependence score, depression score, body mass index, perceived stress, social smoking influences, *social ties, neighborhood cohesion, neighborhood smoking prevalence, neighborhood stress*, and time dependent covariates of self efficacy, spiritual well-being, social support, and *cessation resources*.

The magnitude of intervention effect sizes (e.g., differences in 7-day point prevalence proportions between TX and C groups, and odds ratios for cessation) will be estimated using 95% confidence intervals (95%CI). Effect size estimates allow evaluation of the "clinical" or practical significance/relevance of the study findings.

Analyses for Secondary Aims.

Aim #2. To evaluate the effect of the *Sister-to-Sister* intervention on individual (self-efficacy, spiritual well-being), interpersonal (social support), and neighborhood (cessation resources) factors and to determine if these factors mediate the effect of treatment on smoking cessation outcomes.

Hypothesis 2.1: As compared to the control group, women receiving the *Sister to Sister* intervention will have greater improvement in individual factors (self-efficacy, spiritual well-being), interpersonal factors (social support), and neighborhood factors (*cessation resources*) at 6-and 12 months.

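### The primary model uses none of the five named prognostic baseline variables, and the supportive adjusted models choose their covariates from the outcome data

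*SAP*

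**What the plan says.** Three places in the SAP bear on covariates.

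- **Preliminary Analysis.** Baseline values are compared between the two conditions for imbalance. The stated use is: "These analyses will identify potential confounding variables to be used as covariates in subsequent analyses". The putative prognostic variables to be examined include "age, income, education, nicotine dependence score, and depression score". No test or threshold for imbalance is given.
- **Analyses for Primary Aim, model paragraph.** The primary GLMM contains treatment, time (6 and 12 months), a random neighborhood effect and a fixed intercept for each neighborhood pair. The test of primary interest is treatment by time. No individual baseline covariate is in the model.
- **Analyses for Primary Aim, covariate paragraph.** In later models covariates are added to see whether the intervention stays associated with cessation. "Each covariate considered for inclusion will be examined individually for a relationship with cessation outcomes"; then "those variables with a p value < .25 will be included in an initial model"; then "the potential confounder variable in the initial model with highest p value will be removed and the model will be run again", with the variable left out if the change in -2 log likelihood is not significant. No level is given for that test. Sixteen candidates are listed, including the five above.

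Under Analyses for Secondary Aims, the Hypothesis 2.1 models also receive additional covariates, by reference back to this text.

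**The concern.** Variables thought to be prognostic are named before the analysis and measured at baseline, so there is no need to let the data decide whether to adjust for them. The SAP nevertheless leaves them out of the primary model and makes their use in the adjusted models depend on p values from the trial.

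Two things are at stake. First, the adjusted model is meant to show that the effect is robust. If its covariates were picked by their relation to the outcome in the same data, its confidence interval treats as known a model that was chosen, and the SAP states no allowance for this. Second, the imbalance rule and the outcome-association rule use different criteria. Because the SAP does not connect them, two analysts could follow it faithfully and report different adjusted models.

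**Working it through.** **Stated figures.** The SAP gives no sample size, power, quit rate or number of neighborhoods, so there is no design figure to reproduce. The only number on this point is the .25 screen.

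**The two rules side by side.** A variable that is imbalanced between arms but has p ≥ .25 against cessation is a covariate under Preliminary Analysis and is excluded under the covariate paragraph. A balanced variable strongly related to cessation is treated the opposite way.

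**Simple probabilities, assuming independent tests.**
- Imbalance flagged at an assumed 0.05 on five variables with no true difference between arms: 1 − 0.95^5 = 0.226 for at least one flag.
- Five pure-noise candidates at p < .25: 5 × 0.25 = 1.25 expected to enter; 1 − 0.75^5 = 0.763 for at least one. This counts entry only. In the simulation below, 0.24 to 0.28 of five noise candidates survived elimination on average.

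**Simulation.** Assumptions, none from the SAP: total N 300 or 600; control quit rate 10%; treatment OR 1 or 2; five independent baseline covariates, each with OR 1.0, 1.3 or 1.5 per SD; 0.05 for the imbalance and elimination tests; one time point; no clustering; 600 runs per setting. The Monte Carlo standard error is √(0.05 × 0.95/600) = 0.009 near 5% and √(0.5 × 0.5/600) = 0.020 near 50%.

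Which covariates are chosen when all five are truly prognostic (treatment OR 1 / OR 2):

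| N | OR per SD | Both rules choose the same set | Screen and elimination keep all five | A flagged variable is left out by the screen and elimination, given a flag |
|---|---|---|---|---|
| 300 | 1.3 | 17.7% / 13.0% | 0.3% / 0.8% | 67.4% / 65.8% |
| 300 | 1.5 | 1.0% / 0.3% | 7.8% / 13.5% | 40.2% / 30.7% |
| 600 | 1.3 | 3.7% / 1.2% | 4.0% / 9.2% | 47.8% / 42.0% |
| 600 | 1.5 | 0.0% / 0.0% | 51.7% / 75.2% | 18.1% / 5.6% |

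Rejection rate for the treatment main effect (unadjusted / five fixed / selected by screen and elimination):

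| N | OR per SD | Treatment OR 1 | Treatment OR 2 |
|---|---|---|---|
| 300 | 1.0 | 0.040 / 0.043 / 0.038 | 0.522 / 0.522 / 0.520 |
| 300 | 1.3 | 0.050 / 0.053 / 0.055 | 0.528 / 0.532 / 0.552 |
| 300 | 1.5 | 0.050 / 0.048 / 0.055 | 0.482 / 0.527 / 0.530 |
| 600 | 1.0 | 0.050 / 0.055 / 0.052 | 0.853 / 0.857 / 0.852 |
| 600 | 1.3 | 0.050 / 0.053 / 0.052 | 0.828 / 0.847 / 0.840 |
| 600 | 1.5 | 0.045 / 0.027 / 0.027 | 0.808 / 0.855 / 0.853 |

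**Reading.** The composition of the adjusted model varies a great deal from trial to trial; its type I error does not. With prognostic covariates, fixed adjustment gains over no adjustment 0.532 − 0.528 = 0.004, 0.527 − 0.482 = 0.045, 0.847 − 0.828 = 0.019 and 0.855 − 0.808 = 0.047. Fixed and selected adjustment have about the same power, so the case against selection rests on having the model settled in advance, not on lost power.

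**The case against.** The strongest reply is that the selection touches only supportive models. This stands. A reader might infer that the primary test is data-selected; it is not, because its terms are fixed before any covariate enters.

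A second reply is that the two rules need not contradict each other. Preliminary Analysis speaks of potential confounders, and the later list contains all five variables, so a descriptive look followed by model building is a possible reading. This also stands in part. The SAP does not state that sequence, and the later candidate list does not depend on the imbalance result. The fair charge is an unstated link between the rules, not a proven contradiction.

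Third, a reader might infer a serious inflation of type I error. The SAP does not support that. A separate simulation (200 women per arm, five prognostic and seven null candidates, no clustering) rejected in 5.8% against 4.3% of null trials, but only if the analyst reports whichever of the unadjusted and selected models is significant, and the SAP contains no such rule. Likewise, the high chance that some candidate passes the .25 screen (1 − 0.75^12 = 96.8% for twelve) supposes that every candidate is noise.

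Fourth, the power gain was simulated for an unclustered main effect at one time point, whereas the primary test is treatment by time with neighborhood effects. A covariate measured once at baseline mainly explains differences between women, so its gain cannot be assumed to carry over to that test.

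Finally, the five variables are called putative and their list is not closed. The fix therefore has to commit to a set; the SAP has not done so already.

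**Conclusion.** The point holds as a minor improvement. The primary GLMM leaves named prognostic baseline variables unused. The adjusted models that are to show whether the intervention effect holds up are selected on the outcome, with intervals that ignore the selection and a second, unconnected rule elsewhere in the SAP.

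The conclusion about specification follows from the text alone and needs no simulation. The size does depend on assumptions: type I error near nominal (0.027 to 0.055 for the selected model) and a main-effect power gain of about 0 to 5 points from fixed adjustment, under an assumed sample size, quit rate and covariate strength, without clustering. Nothing here shows that the primary test is biased or invalid, or that it would gain power.

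**What to change.** - Name one baseline set in advance: age, income, education, baseline nicotine dependence and baseline depression. Enter it as fixed effects in the Aim 1 GLMM and use the same set for Hypothesis 2.1.
- In Preliminary Analysis, keep the baseline comparison as description and delete its role in choosing covariates.
- In the covariate paragraph, delete the .25 screen and the backward elimination.
- Report the model without these covariates as a sensitivity analysis.
- If a neighborhood-level variable is also wanted, decide that at the same time and not from the results.

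A baseline-only set has a further benefit. The present candidate list includes four time-dependent variables (self-efficacy, spiritual well-being, social support, cessation resources) that are also the Aim 2 mediators, and adjusting for them can remove part of the treatment effect.

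The cost is mainly SAP wording, since the SAP already plans to compare these variables at baseline. Missing baseline values need simple imputation. Odds ratios become conditional on the covariates, so they will differ somewhat from the unadjusted ones even without confounding, and the text should say so.

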To evaluate the relationships between intervention outcomes and intervention status (TX or C), we will use a generalized linear mixed models (GLMM) approach (*or equivalently hierarchical linear models [HLM], random regression models [RRM], or mixed effects models [MEM]*) with treatment assignment as the primary independent variable and measures of

effectiveness as the dependent variable [146]. This approach accommodates a wide range of distributional assumptions for continuous and categorical outcome variables, including binary (e.g., smoking cessation/no cessation - the primary outcome), count, and ordinal measures, as well as multilevel data such as longitudinal measurements on subjects and a possible cluster effect within neighborhoods [143,146]. These analyses allow for measurement of subjects at different time points, missing data, and time varying or invariant covariates.

In the GLMM analyses, treatment (TX vs C) and measurement time (6 months and 12 months) will be included as a fixed effect, a term representing neighborhood (the cluster effect) will be included in the model as a random effect in order to account for correlation among women within the same neighborhood, *with a pair-specific fixed intercept parameter to represent each neighborhood pair* [148]. The statistical test of primary interest will be the F-test for the treatment x time interaction, which will reflect a difference in change between the intervention and control groups over the course of the study.

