Hypothesis 2.2: Positive changes in individual factors (self-efficacy, spiritual well-being), interpersonal factors (social support, and neighborhood factor (*cessation resources*)) will mediate the effect of the 6- and 12-month cessation outcomes in women receiving the *Sister to Sister* intervention.

A generalized linear mixed models (GLMM) approach, as described for the Primary Aim, will be used for Aim 2. To examine the effect of treatment (TX vs C) on individual factors (self-efficacy, spiritual well-being), interpersonal factors (social support), *and neighborhood factors (cessation resources)* [Hypothesis 2.1], each of the individual variables within the factors will be used individually as the outcome (dependent) variables in the GLMM. As described above, treatment and measurement time will be considered fixed effects, and neighborhood will be

considered a random effect, with a *pair-specific fixed intercept parameter* to represent each neighborhood pair. Additional covariates, as described above, will be added to the model to determine the effect of treatment on these outcomes adjusted for the effect of the covariates.

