The analyses for Hypothesis 2.2 address the question of whether the individual (self-efficacy, spiritual well-being), interpersonal (social support), and neighborhood factors (cessation resources) explain (mediate) the relationship between the outcome (6- and 12-month cessation) and the intervention (Sister-to-Sister). In mediator analyses, it is posited that variation in a given independent variable (intervention) accounts for variation in the mediators (self-efficacy, spiritual well-being, social support, cessation resources) and variations in mediators account for variations in outcome (6-and 12-month cessation). For these analyses, we will follow the methods of Baron and Kenney [149], Holmbeck [150], and Kraemer [151]. GLMM analyses as outlined above will evaluate the relationship between the outcome (6- and 12-month cessation) and the intervention (Aim 1). Next, the relationship between intervention and the putative mediator variables (self-efficacy, spiritual well-being, social support, cessation resources) will be evaluated as described for Hypothesis 2.1. Finally, the mediating effect of self-efficacy, spiritual well-being, social support, cessation resources on a significant treatment effect will be evaluated in a GLMM model that simultaneously regresses treatment (TX vs C) and the putative mediating variables on outcome (smoking cessation). A significant smoking cessation/treatment relationship that becomes nonsignificant following the addition of the putative mediator covariable suggests that the latter accounts for (mediates) the former observed relationship. For example, we conclude that the relationship between treatment and smoking cessation is mediated by self efficacy if the variable representing self efficacy is significant and a previously significant treatment effect becomes nonsignificant in the multivariable model containing both.

102,10:1513-1684.

144. Little RJA, Rubin DB (1987) *Statistical Analysis with Missing Data*. 1987. J. Wiley & Sons, New York.

145. Little RJA, Rubin DB (1987) *Statistical Analysis with Missing Data*. 1987. J. Wiley & Sons, New York.

146. Gibbons R. *Longitudinal Data Analysis*. 2006. John Wiley and Sons, Inc. New York.

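### The adjusted Aim 1 analysis treats the four Aim 2 mediators, at follow-up, as potential confounders, so it can remove the part of the treatment effect that works through them

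*SAP*

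**What the plan says.** All references are to the SAP.

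**Analyses for Primary Aim.** The main model has treatment and time as fixed effects, neighborhood as a random effect and a fixed intercept for each neighborhood pair. "The statistical test of primary interest will be the F-test for the treatment x time interaction". Further analyses then add covariates "to examine whether the intervention remained statistically and clinically associated with cessation after controlling for the potential covariates". Candidates are screened one at a time against cessation, and "those variables with a p value < .25 will be included in an initial model". In backward elimination, "the potential confounder variable in the initial model with highest p value will be removed" and stays out if model fit does not worsen significantly. The list begins with demographic, dependence, depression and neighborhood variables. It ends with "time dependent covariates of self efficacy, spiritual well-being, social support" and cessation resources.

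**Analyses for Secondary Aims.** Aim 2 studies the effect of the intervention on self-efficacy, spiritual well-being, social support and cessation resources, and sets out "to determine if these factors mediate the effect of treatment on smoking cessation outcomes". Hypothesis 2.1 expects treatment to improve all four at 6 and 12 months. For those models, "Additional covariates, as described above, will be added to the model to determine the effect of treatment on these outcomes". The Hypothesis 2.2 analysis regresses cessation on treatment and the same four factors. It reads a treatment effect that loses significance, alongside a significant factor, as mediation.

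**The concern.** The SAP gives the same four variables two incompatible roles. In the Aim 1 adjustment they are potential confounders to be controlled. In Aim 2 they are consequences of treatment that carry its effect. A variable measured after assignment that treatment is expected to change does not confound the treatment comparison. Conditioning on it removes the mediated part of the effect and leaves at most a direct effect, which is itself open to confounding between the factor and cessation.

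The adjusted model therefore cannot say whether the intervention effect holds up, which is its stated purpose. The better the intervention works through its intended route, the worse it will look there. Loss of significance would count against the intervention under Aim 1 and in favor of Hypothesis 2.2, and the SAP has no rule for choosing between these readings. The adjusted Hypothesis 2.1 estimates could be weakened in a similar way if each factor is adjusted for the other three.

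**Working it through.** **1. Compare the lists.** The SAP states no sample size, quit rate or mediator effect, so there is no planned figure to reproduce.

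| Factor | Aim 1 adjustment | Aim 2 |
|---|---|---|
| Self-efficacy | time-dependent covariate | outcome (2.1), mediator (2.2) |
| Spiritual well-being | time-dependent covariate | outcome (2.1), mediator (2.2) |
| Social support | time-dependent covariate | outcome (2.1), mediator (2.2) |
| Cessation resources | time-dependent covariate | outcome (2.1), mediator (2.2) |

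The overlap is four of four. The time-dependent label separates these four from the rest of the list, and nothing limits them to baseline values.

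**2. Size of the loss if a factor is in the model (all inputs assumed).** Take one factor M, normal with SD 1, one time point and no clustering. Treatment T shifts M by d. The model is logit P(quit) = a + cT + bM, with a set to give control quit rates of 5%, 8%, 10% and 15%. The odds ratio without M comes from averaging P(quit) over M in each arm. With M in the model it is exp(c). The share kept is c divided by the log odds ratio without M.

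| Scenario | d | b | c | OR without M | OR with M | Share of log-OR kept |
|---|---|---|---|---|---|---|
| Weak | 0.3 | 0.3 | 0.65 | 2.07-2.09 | exp(0.65) = 1.92 | 88-89% |
| About half | 0.5 | 0.8 | 0.40 | 2.07-2.14 | exp(0.40) = 1.49 | 52-55% |
| Full | 1.0 | 0.8 | 0 | 2.07-2.14 | exp(0) = 1.00 | 0% |

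For example, in the half case 0.40 / ln(2.07) = 0.55. Sample size hardly matters: in simulated trials with a 9% control rate, the half case gives an adjusted odds ratio of 1.52 at 200 per arm and 1.50 at 600.

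**3. Does the selection procedure keep the factor?** At an assumed 200 per arm and 9% control rate, the p < .25 screen admits it in 88% of simulated trials (weak) to nearly 100% (half, full). A second simulation applied both steps: the screen, then a likelihood-ratio test at an assumed .05, since the SAP gives no level. It used 200 per arm, a control quit rate of about 10% and 1,000 replicates per row.

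| d | b | c | Factor retained | OR without M | OR after selection | Significant, without M | Significant, after selection |
|---|---|---|---|---|---|---|---|
| 0 | 0.7 | 0.8 | 99.5% | 2.13 | 2.23 | 76% | 79% |
| 0.5 | 0.2 | 0.7 | 28% | 2.24 | 2.13 | 77% | 69% |
| 0.3 | 0.7 | 0.6 | 99.6% | 2.18 | 1.85 | 79% | 54% |
| 0.5 | 0.7 | 0.45 | 99.7% | 2.16 | 1.60 | 76% | 35% |
| 0.5 | 1.0 | 0.3 | 100% | 2.08 | 1.38 | 77% | 18% |
| 0.8 | 1.0 | 0 | 100% | 2.05 | 1.02 | 75% | 4% |

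The first row is the control case: when treatment does not move the factor, nothing is lost. The procedure tends to keep exactly the factors that carry the most effect, because those predict cessation best.

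**4. Hypothesis 2.1.** Suppose all four factors shift equally and share a within-arm correlation r. Regressing one on the other three gives each a coefficient of r/(1 + 2r). The share of its treatment effect kept is then 1 - 3r/(1 + 2r) = (1 - r)/(1 + 2r).

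- r = 0: 1/1 = 100%
- r = 0.1: 0.9/1.2 = 75%
- r = 0.3: 0.7/1.6 = 44%
- r = 0.5: 0.5/2.0 = 25%

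**The case against.** The overlap itself is not in dispute. The case on the other side concerns reach and size.

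- **These are further analyses.** The primary test carries no such covariates and no success criterion rests on the adjusted model. This stands, and it limits the severity. The adjusted model is still the plan's stated check on whether the effect holds up.
- **The illustration is a main effect at one time point, while the plan tests treatment by time.** This stands. A factor shifted equally and acting equally at both visits would lower the main effect but need not much change the interaction. The figures bear on the odds ratios that the SAP will report, not on the interaction.
- **Screening alone overstates the weak case.** This stands. With a likelihood-ratio step at .05 added, the weak factor of step 2 is admitted by the screen in 88% of trials but retained in only 52%, and the odds ratio moves from 2.09 to 1.98. The half and full cases are retained about 100% of the time.
- **The Aim 1 and Hypothesis 2.2 models are not identical.** The first is stepwise and may hold many other covariates. The second also requires a significant mediator. This is true, but the shared core is treatment plus the same factors, and loss of the treatment effect is still read in opposite ways.
- **Preliminary Analysis already offers a baseline route to covariates.** It does, through baseline imbalance, but it does not take the four factors off the Aim 1 list.
- **The carry-over to Hypothesis 2.1 is ambiguous.** This stands. The text does not say which covariates enter when a factor is the outcome, so that loss is a possibility, and its percentages assume all three other factors are retained.

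**Conclusion.** The concern holds: the covariate list is wrong as written. Four post-assignment variables that the trial expects treatment to change are placed among potential confounders, and no text limits them to baseline or excludes them. The direction of the error follows from the SAP's own hypotheses.

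Its size is conditional on treatment moving a factor, the factor predicting cessation and the selection keeping it. Under the assumed inputs the adjusted odds ratio falls from about 2.1 to between 1.9 and 1.0. It scarcely moves when the factor is a weak predictor that selection often drops. The primary treatment-by-time test is not affected. This should be corrected, but it does not threaten the primary inference.

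**What to change.** - In Analyses for Primary Aim, delete the four time-dependent factors from the covariate list, or replace them with their baseline values. State that only baseline values may enter adjusted treatment-effect models. The other listed covariates can stay, at baseline values.
- Under Hypothesis 2.1, apply the same limit to the additional covariates.
- State that follow-up values of the four factors are used only as outcomes for Hypothesis 2.1 and in the mediation models for Hypothesis 2.2.

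The cost is SAP wording only. The Hypothesis 2.2 models stay as they are and no analysis is lost.

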Premature exits (drop-outs) and missing data. *In order to minimize potential bias due to missing observations, we will carefully document why data are missing, which will involve contacting via telephone, if necessary, those who do not return for follow-up assessments to attempt to ascertain smoking status, and reason(s) for dropout. We will adopt several approaches to dealing with missing data for the ITT analysis set. For the primary dichotomous cessation outcomes, we will impute outcome status in two ways: (1) by considering dropouts as smokers, and (2) using a stochastic regression imputation developed by Hedeker [143] taking different source of variation into account. For analyses of continuous variables using a single outcome (e.g., change from baseline in nicotine dependence score), we will use the multiple imputation methods of Little [144] and Rubin [145]. For longitudinal data, where appropriate, we will employ longitudinal data methods (e.g., mixed models, random regression, or hierarchical linear models) which allow for missing data [143,146]. We will carry out sensitivity analyses by comparing the results of analyses using different methods of imputation to evaluate the role of missing data in the study's conclusions. The implications of the sensitivity analyses will be discussed in presentations of study findings. In addition, we will model the dichotomous outcome, missing/not missing end-of-study score, using logistic regression to determine if "missingness" is related to treatment group and/or initial level of the given outcome variable (baseline score). We will also use information on drop-outs as one of the outcome measures of effectiveness of the interventions being compared. We will make every attempt to keep subjects in the study and to obtain required measurements.*

Analyses for Primary Aim.

Aim #1. To test the effectiveness of a multi-level intervention (*Sister to Sister*) on smoking cessation outcomes in female smokers residing in public housing neighborhoods.

Hypothesis 1.1: As compared to the control group, women receiving the *Sister to Sister Intervention* will have higher 7-day point prevalence quit rates at 6-and 12-months.

Hypothesis 1.2: As compared to the control group, women receiving the *Sister to Sister Intervention* will have higher 6- and 12-month prolonged abstinence.

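### Hypothesis 2.1 claims greater improvement in each factor, but its model prespecifies no baseline value of that factor and does not say which test decides it

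*SAP*

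**What the plan says.** All references are to the SAP.

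- **Analyses for Secondary Aims, Hypothesis 2.1.** Women in the intervention group "will have greater improvement in individual factors (self-efficacy, spiritual well-being), interpersonal factors (social support"; the list then continues to cessation resources. The hypothesis refers to 6 and 12 months.
- **The model for Hypothesis 2.1.** "A generalized linear mixed models (GLMM) approach, as described for the Primary Aim, will be used for Aim 2". The stated purpose is "To examine the effect of treatment (TX vs C) on individual factors" and on the other factors. The separate variables "will be used individually as the outcome (dependent) variables in the GLMM". The terms are then restated: "As described above, treatment and measurement time will be considered fixed effects", with neighborhood as a random effect and a fixed intercept for each pair.
- **Analyses for Primary Aim, to which this refers back.** There, "treatment (TX vs C) and measurement time (6 months and 12 months) will be included as a fixed effect". One test is named: "The statistical test of primary interest will be the F-test for the treatment x time interaction". The SAP explains this test as showing whether the groups change differently during the study.
- **Covariates.** The list in Analyses for Primary Aim names the four factors only as time-dependent covariates. Candidates are screened at p < .25 against cessation. The lists are open, so a baseline factor value is not excluded, but nothing ensures that it enters.
- **Premature exits and missing data.** The phrase "change from baseline in nicotine dependence score" appears only as an example of a continuous outcome for imputation. Nicotine dependence is not one of the Hypothesis 2.1 factors.

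**The concern.** Improvement means change from a starting point. The model for Hypothesis 2.1 has no starting point: baseline is not a time level, not part of a change score and not a prespecified covariate. The section also names no test, so the analyst must choose one, and the choices can give opposite answers on the same data. An SAP should settle that choice before results are seen.

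At stake are the conclusion for each of the four factors and, to a modest extent, the treatment-to-mediator step of Hypothesis 2.2, which reuses this model.

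**Working it through.** The SAP gives no sample size, ICC, effect size or power, so there is no figure of its own to reproduce. The work is to set out the possible readings and size the consequence of each.

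**Reading 1: the Primary Aim interaction test is carried over.** Let d6 and d12 be the differences between intervention and control at 6 and 12 months. With those two time levels only, the interaction is

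d12 − d6.

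For a gain d reached by 6 months and held, this is d − d = 0, whatever the size of d, the ICC or the sample size. The test then rejects only at its type I error rate. A simulation check (8 pairs, 25 women per neighborhood, ICC 0.02, held gain 0.25 SD, 10,000 runs) gave rejection in 4.8%, 5.1% and 5.4% of runs at visit correlations 0.3, 0.5 and 0.7. The test responds only if the gain changes between visits, and it does so equally in both directions. Ignoring clustering, with 200 women per arm and correlation 0.5, power is 0.705 both for a gain growing from 0.25 to 0.5 SD and for one fading from 0.5 to 0.25 SD.

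**Reading 2: the treatment effect on follow-up levels, averaged over 6 and 12 months.** Under random assignment the expected baseline difference is 0, so a difference in follow-up level estimates the difference in improvement without bias. What is lost is precision.

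Assumed inputs, none from the SAP: SD 1; correlation r between any two visits of 0.3, 0.5 or 0.7; 8 neighborhood pairs; 25 women per neighborhood; held gain 0.25 SD; ICC 0.02; the same neighborhood effect at both visits; adjustment acting only within neighborhoods; two-sided 5% test.

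Variance of a neighborhood mean:
- unadjusted: V = (1 − ICC) × (1 + r)/2 ÷ 25 + ICC
- adjusted for baseline: V = (1 − ICC) × [(1 + r)/2 − r²] ÷ 25 + ICC

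SE = √(2V/8); power is from the noncentral t on 8 pair differences (7 df).

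| r | V unadjusted | V adjusted | Variance cut | Power unadjusted | Power adjusted |
|---|---|---|---|---|---|
| 0.3 | 0.98 × 0.65/25 + 0.02 = 0.0455 | 0.98 × 0.56/25 + 0.02 = 0.0420 | 8% | 52% | 56% |
| 0.5 | 0.98 × 0.75/25 + 0.02 = 0.0494 | 0.98 × 0.50/25 + 0.02 = 0.0396 | 20% | 49% | 58% |
| 0.7 | 0.98 × 0.85/25 + 0.02 = 0.0533 | 0.98 × 0.36/25 + 0.02 = 0.0341 | 36% | 46% | 64% |

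The same formulas at other ICCs give variance cuts of 10%, 25%, 44% at ICC 0.01 and 5%, 12%, 23% at ICC 0.05. The gain shrinks as variation between neighborhoods dominates.

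**Reading 3: baseline is a time level.** A held gain is then detectable through the interaction. Ignoring clustering, with 100 to 200 women per arm, a held gain of 0.3 to 0.5 SD and r from 0.3 to 0.7, power runs from 0.44 to above 0.99.

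**The case against.** The strongest reply is that the interaction test is not what this section asks for. It borrows an approach, restates the fixed, random and pair terms, and mentions neither the interaction nor its F-test. It describes its target twice as the effect of treatment. The test of primary interest belongs to the Primary Aim text. This stands: reading 2 is the more natural one, and the harm under reading 1 is conditional. A reader might infer that the plan as written cannot detect a sustained gain in these factors. The document does not support that, because it never says that the interaction decides Hypothesis 2.1.

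A second reply is that the authors meant baseline to be a time level, since they describe the interaction as showing a difference in change over the study, and the hypothesis speaks of improvement. That may have been the intent. But the time levels are written as 6 and 12 months, and the Hypothesis 2.1 text refers back to them without adding baseline.

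A third reply is that omitting baseline is no error in a randomized comparison. This also stands. A reader might infer bias; under random assignment there is none, and the cost is precision for a secondary aim.

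Finally, separate 6- and 12-month contrasts would not be a clear gain. At ICC 0.02 the adjusted 6-month contrast has power 45%, 49%, 58%, against 52%, 49%, 46% for the unadjusted average, and the rule for success across two time points would still be open. The fix therefore uses the averaged effect.

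**Conclusion.** The point holds as a gap in specification. The hypothesis is about improvement, the model is for follow-up levels with no prespecified baseline value, and the deciding test is not named.

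The zero contrast under reading 1 is algebra and needs no assumed figure, but it applies only if that test is carried over. Under the favoured reading 2, the cost is the precision loss tabulated above; those sizes rest wholly on assumed inputs, and they do not cover cessation resources if that factor is measured once per neighborhood.

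The effect on mediation is modest, because the worked decision rule for Hypothesis 2.2 does not require the treatment-to-mediator path to be significant.

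This is a cheap improvement. It ranks below the same interaction-test problem in Analyses for Primary Aim, where the test is named outright for the primary outcome.

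**What to change.** Add to the Hypothesis 2.1 paragraph in Analyses for Secondary Aims:

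> Each Hypothesis 2.1 model includes the baseline value of the factor being modelled as a prespecified covariate (for cessation resources, at the level at which it is measured). Hypothesis 2.1 is tested for each factor by the treatment effect averaged over 6 and 12 months, not by the treatment x time interaction; the 6- and 12-month contrasts are reported with 95% CIs.

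Use the same model for the treatment-to-mediator step of Hypothesis 2.2.

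Cost: two sentences, one extra parameter per model and a rule for missing baseline values. No new data are needed if the factors were measured at baseline. The claim of improvement presupposes that they were, but the SAP does not show the assessment schedule.
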